A Neurokinin-1 Receptor Antagonist for the Treatment of Pruritus in
Patients With Epidermolysis Bullosa

Study Protocol and Statistical Analysis Plan

NCT03836001

March 25, 2021

1. Title: A Phase 2 trial of Neurokinin-1 Receptor Antagonist for the Treatment of Itch in Epidermolysis Bullosa Patients

2. PI: [name]

Co-PI: [name], PhD

3. Funding sources for this project:

Epidermolysis Bullosa Research Partnership (EBRP) – providing funding (SPO # [REDACTED])
Menlo Therapeutics, Inc. – providing study medication

4. Abstract:

This is a follow-up study to a prior pilot phase 2 trial conducted here at Stanford and will assess the effect of serlopitant (5 mg daily) on EB-related itch in adolescents (≥ 13 y.o.) and adults with EB. We will evaluate the degree of itch relief in participants taking serlopitant as compared to placebo. This will be determined by comparing the proportion of participants with 3 point or greater reduction in average daily itch severity as measured by numeric rating scale (NRS) score following two months of treatment. Secondary aims include continuous change in average daily NRS and worst itch NRS over time, proportion of participants achieving 2-point and 4-point reductions in average itch severity following two months of treatment and change in median NRS as compared to baseline. Finally, we will assess the safety profile of serlopitant in study participants. It is our hope that serlopitant will reduce itch in adolescents and adults with EB.

5. General background:

Management of chronic pruritus is notoriously challenging for patients with epidermolysis bullosa (EB). In a comprehensive survey of 146 EB patients, itch was reported as the most bothersome EB symptom, ranking higher than acute or chronic pain or problems eating.¹ Furthermore, pruritus can induce an itch-scratch-blister cycle, which can exacerbate existing wounds or induce new wounds.² There have been no new drugs for chronic pruritus, and the current management of pruritus in EB with antihistamines and topical steroids only minimally relieve itch.³

Recent insights into the underlying pathogenesis of pruritus have revealed that substance P and its receptor, neurokinin-1 (NK1), are key transmitters of the itch signal. By inhibiting the NK1 receptor, serlopitant blocks the transmission of itch from the skin to the central nervous system. NK1 receptor antagonists (aprepitant and serlopitant) were originally tested in clinical trials as antiemetics and medications to treat overactive bladder.¹ Since 2005, NK1 receptor antagonists have been evaluated in more than a dozen completed Phase 1 studies and two Phase 2b studies (N=300 participants).

Serlopitant was evaluated in a multi-center, double blind, 6-week randomized trial of 257 adults with chronic pruritus for the treatment of severe, chronic pruritus.² There was a statistically significant and dose-dependent reduction in pruritus at the end of six weeks at the 1 mg and 5 mg doses. Participants in this study had chronic pruritus due to a variety of dermatologic, neuropathic, and psychogenic causes that was unresponsive to topical steroids and antihistamines. Serlopitant was well tolerated and safe in doses up to 5 mg daily, and there were no treatment related serious adverse events. When assessed with a visual analog scale (VAS), pruritus was significantly reduced in both the 1 mg ($p = 0.001$) and the 5 mg ($p = 0.002$) groups compared to placebo. After 6 weeks of treatment, nearly 70% of participants taking 5 mg of serlopitant reported a 2-point reduction in VAS while nearly 50% of participants reported a 4-point decrease in VAS.

We recently reported the results of a prior phase 2 randomized, double blind, placebo-controlled trial evaluating the effects of serlopitant over 8 weeks for treatment of EB-related itch.³ Participants were age > 13 years old,

with any EB subtype. Although the 14 participant trial was only powered to detect large differences in numeric rating scale (NRS) itch scores, we observed a small magnitude reduction in NRS itch score over time in favor of serlopitant relative to placebo (0.08 point/week comparative reduction) although this difference did not meet statistical significance ($p=0.11$). This was equivalent to a 0.64-point reduction in the NRS itch score (rated 0-10) by the end of the active treatment period. In post-hoc analysis, we found a significant majority of participants in the serlopitant arm (86%) experienced at least a 1-point reduction in NRS score by end of treatment. More participants in the active group (43% vs. 14%) achieved at least a 3-point reduction in NRS itch score by the end of treatment as compared to placebo, although this was not statistically significant ($p=0.35$). Serlopitant was well tolerated, with no new safety signals observed.

6. Study design:

This is an investigator-initiated, single-center, randomized, double-blind, placebo controlled, parallel arm trial evaluating the effects of serlopitant at 5 mg by mouth daily on EB-related itch. Eligible participants must have a clinical diagnosis of EB and average daily pruritus rated at least 5 based on a 0-10 Numeric Rating Scale (NRS) persistent for at least 6 weeks.

We aim to recruit at least 40 participants, age 13 and older, of all EB subtypes. Participants will be assigned to placebo or serlopitant in a 1:1 ratio. Participants randomized to serlopitant will receive a loading dose of serlopitant 15 mg PO once, followed by serlopitant 5 mg PO daily for 2 months. This dosing regimen is identical to that investigated during our pilot phase 2 trial.

After completing the double-blind phase of the trial, all participants will undergo one month of wash-out before being offered the option of participating in an open label extension phase with serlopitant 5 mg PO daily for continued monitoring of toxicity and efficacy. This extension phase will be 12 months for participants enrolled prior to May 2020, and 3 months for participants enrolled after May 2020, due to drug availability.

Due to the potential pain and skin injury that can be incurred with travel for participants with more severe EB subtypes, this trial is intentionally designed to minimize the number of in-person clinic visits through use of home itch diaries and phone follow-up, as recommended by the FDA in their EB-specific guidance document.⁴

7. Efficacy Endpoints:

Based on the data from our pilot study, the primary statistical endpoint will be the proportion of participants who achieve at least a 3-point reduction in average daily NRS itch severity from baseline at the end of the two-month double-blind phase.

Secondary endpoints will include:

1. Comparative weekly change in daily worst-itch NRS during the double-blind phase
2. Safety, as measured by adverse events during the course of the double-blind and open label phases of the trial. These will also include changes in ECG parameters and safety labs following drug exposure.
3. Comparative weekly change in average daily NRS itch severity during the double-blind phase
4. Proportion of participants who achieve at least 2 and 4-point reductions in average daily NRS itch severity from baseline at the end of the double-blind phase
5. Proportion of participants who achieve at least a 30% or 50% reduction in average daily NRS itch severity from baseline at the end of the double-blind phase
6. Change in participant-reported outcomes of global assessment of change in itch and overall improvement as measured by static participant assessment of itch, participant global assessment of change in itch severity, and caregiver global assessment of change in itch severity.

The Stanford EB Itch Survey also captures additional measures related to symptoms during dressing changes, sleep quality, and other quality of life measures which may be explored.

Additional exploratory endpoints will revolve around mean comparative change in wound surface areas, comparative change in NRS itch severity at target wounds, and the change in median NRS score by group from baseline at month 1, month 2, and month 3.

We will also assess participant and caregiver perceived change in wound size and number, and pain as measured with the Wong-Baker FACES⁵ scale, and changes in quality of life assessed with ItchyQoL,⁶ and the Dermatology Quality of Life Index (DLQI).⁷

Further exploratory analysis comparing multiple pruritus-related instruments will be explored to determine the most appropriate measures of pruritus for this participant population.

8. Inclusion / Exclusion Criteria:

Inclusion criteria:

1. Males or females who are at least 13 years of age.
2. Willing and able to understand and sign informed assent/consent. Adolescents will need a parent or guardian willing and able to give consent.
3. Clinical diagnosis of epidermolysis bullosa (Dystrophic EB, EB Simplex, Junctional EB, or Kindler syndrome).
4. History of chronic pruritus of at least 6 weeks in duration
5. NRS pruritus score of at least 5 on average itch score in the past 24 hours at Screening Visit or Pre-Screening Phone Call
6. Female participants of childbearing potential, must have a confirmed negative urine pregnancy test prior to study treatment and be willing to use effective contraception for the duration of the trial
7. Judged to be in good health based upon the results of a physical examination, medical history, and safety laboratory tests.

Exclusion criteria:

1. Have any medical condition or disability that would interfere with the assessment of safety or efficacy in this trial or would compromise the ability of the participant to travel to Stanford, to undergo study procedures, or to give informed consent.
2. History of sensitivity to any components of the study material.
3. Females of childbearing potential who are unwilling to use adequate contraception or who are breast feeding.
4. Have any chronic or acute medical condition that, in the opinion of the investigator, might interfere with the study results or place the participant at undue risk.
5. Have chronic renal disease, i.e., serum creatinine greater than 2 times the upper limit of normal.
6. Have chronic liver disease, i.e., AST or ALT greater than 2 times the upper limit of normal. Participants with hepatitis B and C who have normal liver function may be enrolled.
7. Have a current malignancy (e.g. Hodgkin's lymphoma, myeloma, B or T cell lymphoma) or blood cell dyscrasia (e.g., polycythemia or myelofibrosis) that could lead to systemic chronic pruritus.
8. History of thyroid cancer, thyroid nodules, inadequately treated thyroid disease, or abnormal TSH or free T4 at screening: TSH >10, TSH > 5 with low free T4, TSH <0.1, TSH < 0.4 with high free T4.
9. Known history of abnormalities in adrenal or pituitary function (pituitary adenoma, adrenal insufficiency, or adrenal nodule).
10. Screening cortisol < 3 mcg/dL
11. Unevaluated abnormalities in cortisol, ACTH, or prolactin.
12. Have pruritus of psychogenic etiology (delusions of parasitosis, obsessive compulsive disorder and major depression) or neuropathic etiology (due to shingles, spinal cord injury or with neurologic deficit).

13. Have pruritus due to urticaria, drug allergy, or infection (such as pityriasis rosacea or tinea or active human immunodeficiency virus [HIV]). Note: Participants with HIV who have undetectable viral load, CD 4 counts >200 cells/cc, and stable retroviral therapy may enroll.
14. Have taken investigational medications within 30 days prior to Screening.
15. Are unwilling to discontinue specific medications that, in the view of the investigator may have significant interactions with the trial drug, for at least 30 days prior to initiation of study and throughout the study period (all severe CYP34A inhibitors - this includes miconazole, delavirdine, conivaptan, clarithromycin, telithromycin, nefazodone, itraconazole, ketoconazole, indinavir, lopinavir, nelfinavir, ritonavir, saquinavir).
16. Are unable or unwilling to maintain their current anti-itch and opioid-based pain medications at a stable dosage through the course of the two months of active treatment (including but not limited to opioid pain medications, antihistamines, tri-cyclic antidepressants, and gabapentin)
17. Started or changed medications, creams, or emollients including over the counter preparations or bath oils specifically for treatment of pruritus within 30 days prior to Screening.
18. Have expressed suicidal ideation with some intent to act in the past 12 months
19. Have any social or medical condition (e.g. alcoholism, drug dependency, psychotic state) that, in the investigator's opinion, might interfere with the participant's ability to comply with the requirements of the protocol.

9. Study visits: (see Appendix, Schedule of Events)

9.A. Screening Visit:

Participants will be pre-screened over the phone prior to the screening visit to assess inclusion criteria. During the screening visit, following informed consent (and assent as applicable for adolescents), medical history, medication history, and relevant medical records will be collected. Vital signs (including weight) will be recorded and a physical examination will be performed.

When obtaining medical history in female participants we will specifically inquire about:

- Menstruation: Amenorrhea (in participants that had previously reached menarche), abnormal menses, significant abnormal vaginal bleeding
- Significant abnormal vaginal discharge.
- Known breast lumps, nipple discharge
- Participants > 40 years old: if they have had previous mammograms, when their last mammogram occurred, if any mammograms have been abnormal.

If any of the above abnormalities are present, they will be evaluated prior to trial entry.

9.A.i. Wound Assessments:

Investigators will quantify and assess affected skin surface area with body map diagrams and photography. Photography may be obtained using the Tissue Analytics smartphone app. This is a HIPAA-compliant app that is able to photograph a wound, measure the wound, and track it over time. Wounds will be classified as chronic open (unhealed for > 12 weeks) or recurrent (heals in < 12 weeks and re-opens).

If applicable, we will identify up to 4 target wounds that meet the following criteria:

- 1) Measure at least 10 cm²
- 2) Wound-specific NRS itch score of at least 5 during the past 24 hours

We will aim to capture the participant's most pruritic wounds as target wounds.⁸ Target wounds will be photographed.

Participants will evaluate the following characteristics of each target wound: average itch in past 24 hours (NRS), worst itch in past 24 hours (NRS), average pain in past 24 hours (Wong Baker FACES Pain Scale). If

the participant's most pruritic wounds do not meet criteria for inclusion as target wounds, we will not photograph any wounds, but will ask participants to evaluate wound characteristics.

9.A.ii. Global Pruritus Assessments:

In addition to the NRS, pruritus will be evaluated with the following questionnaires:

- 1) Stanford EB Itch Survey
- 2) Itch Man⁹
- 3) Dermatology Quality of Life Index (DLQI)⁷
- 4) ItchyQoL⁶
- 5) Leuven Itch Scale¹⁰
- 6) Static Participant Global Assessment of Itch Severity
- 7) PROMIS Scales – Pediatric versions for participants <18y
- 8) Itch Controlled Days Questionnaire

9.A.iii. Electrocardiogram:

Baseline electrocardiogram (ECG) will be performed, using our established technique using non-stick pads to prevent injury due to electrodes. The overall ECG assessment (abnormal or normal) will be summarized. We will review whether the participant has had previous echocardiogram and the results will be included in the chart.

9.A.iv. Safety Laboratory Assessments:

We will assess the following labs:

- 1) Complete blood count (CBC)
- 2) Complete metabolic panel (CMP)
- 3) Urinalysis
- 4) Urine pregnancy test (if applicable)
- 5) Thyroid stimulating hormone (TSH)
- 6) Free T4
- 7) Cortisol
- 8) ACTH
- 9) Prolactin

Labs will ideally be drawn in the morning. Participants with low cortisol will be referred to their primary care physician or endocrinologist for further evaluation which may include AM cortisol level or dynamic testing with a standard cosyntropin stimulation test. If prolactin is abnormal, participants will be required to have this evaluated prior to study participation.

At the discretion of the investigator, labs drawn by non-study providers within 60 days of screening and baseline may be substituted for the trial screening labs so long as they include the same studies of interest. This is in order to reduce unnecessary skin trauma and a potentially psychologically traumatic blood draw.

9.A.v. Home Diaries and Preparation for Month 1:

Participants will be asked to complete a daily itch diary with their average itch score (NRS) over the past 24 hours and their itch score during dressing changes or bathing (NRS). This may either be an online diary (administered securely through REDCap¹¹) or a paper diary, based on participant preference.

Female participants of childbearing potential (including participants that have not yet undergone menarche) who are not using hormonal contraception will be provided with a menstrual diary to complete.

Participants will be provided with a lab requisition form to have their Month 1 labs drawn at a Quest lab near their home.

Participants will also be specifically educated about the signs and symptoms of adrenal insufficiency (e.g. fatigue, abdominal pain, dizziness, etc.) and will be instructed to report these symptoms to study investigators.

9.B. Baseline Visit (Within 30 Days of Screening):

Participants will return to Stanford for a baseline visit within 30 days of screening. Per the discretion of the investigator(s), screening and baseline may be combined into the same visit. Outside of this window, participants will be considered a “screen fail” and would have to undergo another screening visit.

9.B.i Eligibility Confirmation and Randomization:

Vital signs, medical history, concomitant medications, ECG results, and safety lab results obtained at screening will be reviewed for eligibility. Once participant eligibility is confirmed, randomization will occur.

9.B.ii. Assessments:

Target wounds will again be characterized and photographed. The study diary will be reviewed to assess participants’ mean daily pruritus rating and variation of itch scores at baseline.

If the baseline and screening visit are combined, participants will be instructed to complete a minimum of 7 days of their nightly itch diary prior to starting medication in order to establish baseline itch severity.

Study medication will be dispensed one week after eligibility is confirmed to reduce confusion about when to begin study medication.

The scheduling of the Month 1 phone call will account for this 1-week lag prior to starting medication.

9.C. Month 1 Phone Call:

Month 1 phone call will occur 30 days after starting the study medication, +/- 14 days.

9.C.i. Safety Laboratory Assessments:

Safety labs will be drawn as early as 10 days prior to scheduled phone follow-up at month 1 following initiation of active treatment. Labs will be drawn at a local laboratory convenient for the participant. They will have the option to have labs drawn at Stanford if they prefer.

At the discretion of the investigator, labs drawn by non-study providers within this time window (1 month after medication initiation, +/- 10 days) may be substituted for the study lab draw, as long as they include the same studies of interest. This is in order to reduce unnecessary skin trauma and a potentially psychologically traumatic blood draw.

Safety labs will include:

- 1) Complete blood count (CBC)
- 2) Complete metabolic panel (CMP)
- 3) Urinalysis
- 4) Urine pregnancy test (if applicable)

Medication will not be sent until safety labs have been reviewed by the investigator. Any abnormal labs will be reviewed by investigator and appropriate follow-up will be initiated as needed.

9.C.ii. Assessments by Phone:

Participants will be queried for any adverse events and changes to concomitant medications or wound dressing regimen. These will be assessed by investigators.

Participants will specifically be asked about any symptoms of adrenal insufficiency (e.g. fatigue, abdominal pain, dizziness, etc.). Participants who report symptoms concerning for adrenal insufficiency will be evaluated with instructions to follow-up urgently with their primary care provider for further evaluation, which should include an AM cortisol. If this is abnormal, we will coordinate with their primary care provider for urgent referral to endocrinology for further evaluation including cosyntropin stimulation testing.

Female participants will specifically be queried regarding abnormal vaginal bleeding (new and different from any related to any known EB wounds in the genital area), new breast findings (not related to EB wounds), expulsion of an intrauterine device or implant, or vaginal discharge. If any of these concerns are identified, the participant will be urgently referred to their primary care provider for further evaluation.

9.C.iii. Assessments via REDCap:

A link will be sent to the participant to complete the following assessments via REDCap:

1. Stanford EB Itch Survey
2. Itch Man

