The proportion of participants achieving 2, 3, and 4-point reductions in average daily NRS with serlopitant at the end of 8 weeks of active treatment will be compared to placebo using Fisher's Exact test. A similar approach will be utilized to compare the proportion of participants achieving at least a 30% or 50% reduction in itch as measured by NRS from baseline at 8 weeks.

We will also measure continuous change in average daily NRS and worst-itch NRS score by group over time. For each participant, we will plot their average itch scores over time before and after drug intervention. For each dosage group, we will use linear regression methods with mixed effects (GLM, SAS) to track the change in itch in each of the groups from baseline.

Furthermore, we will evaluate monthly change in median NRS itch scores by group as compared to baseline, which will enable evaluation of durability through assessment of NRS itch scores at month 3 of washout.

Primary and secondary endpoints will be performed on an intention to treat basis. This study will provide the effect size, standard deviation and range of itch scores in EB participants in order to properly power a phase 3 trial.

11. Safety Assessment and Monitoring

11.A. Pregnancies and Contraception Requirements for Females

For the purposes of this study, a female of childbearing potential is defined as any female who has experienced menarche and is pre-menopausal, unless permanently surgically sterile (e.g., hysterectomy, bilateral salpingectomy, bilateral oophorectomy). A postmenopausal state is defined as no menses for 12 months without an alternative medical cause in a previously menstruating female. We note that many adolescents with severe subtypes of epidermolysis bullosa have may significantly delayed age of menarche.

For the purposes of this study, all female participants of childbearing potential must use highly effective contraception (i.e. pregnancy prevention method with a failure rate of <1% per year) from the time of the Screening visit until 2 weeks after the last dose of study drug. This includes the use of one or more of the following acceptable methods:

1. Surgical sterilization (e.g., bilateral tubal occlusion or ligation, hysterectomy, bilateral salpingectomy, bilateral oophorectomy).

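### Secondary endpoint 1 needs a daily worst-itch NRS, but neither diary item the protocol names is worst itch

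*Combined protocol and SAP*

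**What the plan says.** Three places commit to a worst-itch score for the participant, followed over time.

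- The abstract: "Secondary aims include continuous change in average daily NRS and worst itch NRS over time".
- Section 7, secondary endpoint 1: "Comparative weekly change in daily worst-itch NRS during the double-blind phase".
- Section 10.C: "We will also measure continuous change in average daily NRS and worst-itch NRS score by group over time". Mixed-effects regression is then to "track the change in itch in each of the groups from baseline".

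Diary content is set out in Section 9.A.v, where the participant's task is: "complete a daily itch diary with their average itch score (NRS) over the past 24 hours and their itch score during dressing changes or bathing". Section 9.B.ii uses this diary for baseline. It is reviewed for "mean daily pruritus rating and variation of itch scores at baseline", and when Screening and Baseline are combined, participants are to "complete a minimum of 7 days of their nightly itch diary prior to starting medication in order to establish baseline itch severity".

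A worst-itch NRS is described as collected only in the wound assessments (Sections 9.A.i and 9.D.i, and footnote 4 to the Schedule of Events). Section 7 places "comparative change in NRS itch severity at target wounds" among the exploratory endpoints.

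**The concern.** The endpoint needs a nightly worst-itch rating for the whole participant, with a pre-dose baseline, so that weekly change can be compared between arms. The text describes no such rating. A site following the protocol to the letter would finish the trial with nothing to analyse for a prespecified secondary efficacy endpoint.

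What is at stake depends on the forms. If the REDCap and paper diaries do carry a worst-itch item, the harm is limited to an unstated data source. If they do not, the ratings cannot be recovered afterwards. The endpoint would then be dropped, restricted to later participants, or replaced by some other itch measure. Without an amendment, that choice could be made after data have been seen.

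**Working it through.** The plan states no figure to reproduce here. The check is to set every described source of itch data against what the endpoint requires.

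| Source | Where described | What is rated | When | Daily worst itch for the participant? |
|---|---|---|---|---|
| Diary item 1 | 9.A.v | 24-hour average itch | Daily | No |
| Diary item 2 | 9.A.v | Itch at dressing change or bathing | Daily | No |
| Wound ratings | 9.A.i, 9.D.i, Schedule footnote 4 | Average and worst itch, per wound | Screening, Baseline, Month 2 | No: per wound, not daily |
| Visit NRS | 9.A.ii; inclusion criterion 5 | 9.A.ii does not say average or worst; criterion 5 is average | Visit or pre-screening call | No |
| Questionnaires | 9.A.ii, 9.C.iii, 9.D.ii, Schedule footnote 5 | No worst-itch NRS item described | Visits and calls | No |

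**Mentions of worst itch as a measure.** Three places state an aim, endpoint or analysis (abstract, Section 7, Section 10.C). Three describe collection (9.A.i, 9.D.i, footnote 4), and all three are at wound level. The two sets do not meet.

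**Could wound ratings stand in?** No. There is no wound rating at Month 1, so each wound gives at most one start-to-end difference and no weekly course. Section 7 also treats target-wound itch as a different endpoint.

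**Scale of the gap, on the text as written.**

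- Worst-itch items among the diary items named: 0 of 2.
- Treatment nights per participant: 8 weeks × 7 = 56 (10.C), or 60 (9.D). Worst-itch entries: 0.
- Minimum pre-dose diary nights when visits are combined: 7 (9.B.ii). Worst-itch entries: 0.
- Over 40 participants: 56 × 40 = 2,240 to 60 × 40 = 2,400 participant-nights, all of which supply average itch and none worst itch. This is the same yes-or-no fact multiplied out. With the ±14-day window of 9.D, the range per participant is 46 to 74 nights.

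**Can the item still be added for everyone?** Section 6 shows that some participants enrolled before May 2020. The longest described path from enrolment to the end of the double-blind phase is:

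- 30 days from Screening to Baseline (9.B)
- 30 days' wash-out of a prohibited medication, if needed (Schedule footnote 12)
- 7 days' dispensing lag (9.B.ii)
- 60 + 14 days to the Month 2 visit (9.D)

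30 + 30 + 7 + 60 + 14 = 141 days. Counting from 30 April 2020, that ends on 18 September 2020. This version is dated 25 March 2021, which is 188 days later. If the windows were followed, those participants had already finished and could no longer supply the item. Their number is not given.

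**The case against.** The strongest objection is that the diary forms and questionnaire items are not reproduced. Protocols often summarise a diary without listing every question, so what is shown is an unstated source and not missing data. That is correct, and it sets the limit of the conclusion. It does not clear the text: 9.A.v lists specific items, and the wound sections name worst itch beside average itch where both are wanted.

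Second, Section 10.B links the diary to worst itch, saying it is kept before bedtime because itch is reported to peak then. This explains when the diary is filled in; the item itself still asks for a 24-hour average.

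Third, 9.A.v is written for the first diary, and the Month 2 and wash-out diaries have no item list. That they hold the same items is an inference. But an item appearing only in a later diary would still lack a pre-dose baseline.

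Fourth, the risk of bias is limited. If no worst-itch data exist, dropping the endpoint cannot be driven by worst-itch results, and 10.A withholds aggregate access from investigators until the last participant completes the randomized phase. This stands in part. The remaining risk is a substitute chosen after other results are known.

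Finally, only one secondary endpoint is involved, and the sample-size calculation does not use it. That is why the point is something that should be fixed and not a threat to the trial's main result.

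**Conclusion.** The concern holds. As written, the plan contradicts itself: it promises a daily worst-itch score analysed from baseline and describes no collection of one. Secondary endpoint 1, one of six, cannot be computed from the data collection described. The primary endpoint and secondary endpoints 3 to 5 are unaffected.

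Confidence is high for the protocol text. Whether data are actually missing is unknown, because it depends on forms outside the documents. The timing argument further assumes that the described visit windows were kept, and it matters only if the item is absent.

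**What to change.** Check the REDCap and paper diary forms first.

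- **If a 24-hour worst-itch item exists:** name it as the source of the endpoint. Cost: one sentence each in 9.A.v and 10.C.
- **If it does not:** add a 0–10 rating of worst itch over the preceding 24 hours to the diary for participants not yet dosed, starting in the pre-dose diary period (the 7 days in 9.B.ii when visits are combined) so that a baseline exists. State that the endpoint covers only those participants, and analyse them in the arms to which they were randomised. Anyone already partway through the pre-dose days will have a shorter baseline, and this should be reported. Cost: one extra question per night, and an endpoint estimated on part of the sample.
- **If no participants, or too few, remain to be dosed:** remove the endpoint from the abstract, Section 7 and 10.C by amendment before the aggregate access described in 10.A, and record that it was planned but not collected. Cost: the endpoint is lost.

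Do not substitute wound-level itch, which is a separate endpoint and is not daily. Do not substitute itch at dressing change or bathing, which is tied to one situation and which the documents nowhere equate with worst itch.
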